### 6.5.2. Hematologic Improvement

Hematologic improvement will be assessed through collection of transfusion records and local hematology parameters.

Both response and HI will be assessed locally by the investigators using modified IWG AML response criteria (Cheson, 2003) and IWG response criteria in myelodysplasia (Cheson, 2006), and retrospectively by a blinded Independent Response Adjudication Committee (IRAC) if the study data will be used for regulatory activities.

### 6.5.3. Survival

Refer to Section 6.3 for survival follow-up.

## 6.6. Pharmacokinetics

Pharmacokinetic sampling for AG-120 will be conducted on all subjects during Phase 1b AG-120 expansion stage as detailed in Table 6.

During Phase 1b AG-120 expansion stage, subjects enrolled in the AG-120 combination treatment arm will undergo intensive PK assessments, in order to evaluate the PK profile of AG-120 when administered with azacitidine. On Days 1 of Cycle 1 and 2, blood samples will be collected at the following time points: pre-dose (within 30 minutes prior to AG-120) and 0.5 hours ( $\pm$  10 minutes), 2 hours ( $\pm$  10 minutes), 3 hours ( $\pm$  10 minutes), 4 hours ( $\pm$  10 minutes), 6

hours ( $\pm$  10 minutes), and 8 hours ( $\pm$  10 minutes) post-dose. Pre-dose blood samples (trough) will also be obtained on C1D15.

During Phase 2 AG-221 randomization stage, the first twelve subjects at selected sites in the AG-221 combination treatment arm will undergo intensive PK assessments (Table 7) over a 24-hour period on C2D1 to C2D2, in order to evaluate the PK profile of AG-221 when administered with azacitidine. Blood samples will be collected at the following time points: pre-dose (within 30 minutes prior to AG-221) and 2 hours ( $\pm$  10 minutes), 3 hours ( $\pm$  10 minutes), 4 hours ( $\pm$  10 minutes), 6 hours ( $\pm$  10 minutes), 8 hours ( $\pm$  10 minutes,) and 24 hours ( $\pm$  10 minutes) post-dose. Pre-dose blood samples (trough) will also be obtained on C3D1.

The subjects not being assessed for intensive PK in the AG-221 treatment arm during the Phase 2 segments will undergo sparse PK samples for measurement of AG-221 concentration (Table 8). Blood samples will be collected at pre-dose (within 30 minutes prior to dosing) and 4 hours ( $\pm$  10 minutes) post-dose on Day 1 of Cycle 2, and pre-dose on Day 1 of Cycle 3.

No PK samples will be collected from subjects who are randomized to the azacitidine alone treatment arm.

The peripheral blood sample should be collected by an in-dwelling catheter or by venipuncture into sample collection tubes. Sample collection kits and supplies will be provided by the sponsor or sponsor-designated vendor. Blood samples for sparse PK should be processed promptly and plasma harvested and stored according to the instructions in the Study Reference and/or Study Laboratory Manual.

## 6.7. Pharmacodynamics, [REDACTED]

Bone marrow, blood [REDACTED] samples for biomarker assessments (pharmacodynamics, [REDACTED]) should be collected according to the Table of Events, in parallel with collection of bone marrow for disease assessment time points. Sample collection, processing, storage, and shipment procedures will be provided in the Study Reference and/or Study Central Laboratory Manual.

Bone marrow and blood will be collected at baseline and during the course of treatment for correlative analyses to provide information on drug mechanisms of action relevant to clinical response. Pharmacodynamic measurements will include assessment of [REDACTED] 2-HG levels in blood and/or bone marrow. [REDACTED]

[REDACTED] Results from these studies will be evaluated in association with parameters of clinical benefit, to determine if biomarkers of response or non-response to treatment may be identified. [REDACTED]

## 6.8. Quality-of-Life

Two instruments, the European Organization for Research and Treatment of Cancer Quality-of-Life questionnaire (EORTC QLQ-C30) and EuroQoL Group EQ-5D-5L, will be used for evaluating HRQoL outcomes.

The EORTC QLQ-C30 ([Aronson, 1993](#)) is a validated quality-of-life measure applicable to subjects with any cancer diagnosis. It is composed of 30 items that address general physical symptoms, physical functioning, fatigue and malaise, and social and emotional functioning. Subscale scores are transformed to a 0 to 100 scale, with higher scores on functional scales indicating better function and higher scores on symptom scales indicating worse symptoms. The EORTC QLQ-C30 is available in many languages. This instrument takes 10 to 15 minutes to administer. The EORTC QLQ-C30 data will be captured using a portable electronic tablet computer. See [Appendix N](#) for an example.

The EQ-5D-5L is a standardized instrument for use as a measure of health outcome. It provides a simple descriptive profile and a single index value for health status, and is applicable to a wide range of health conditions and treatments. The EQ-5D-5L is available in many languages and it takes approximately 5 minutes to complete. EQ-5D-5L data will be captured using a portable electronic tablet computer. See [Appendix O](#) for an example.

It is important that every subject completes all assessments of EORTC QLQ-C30 and EQ-5D-5L at every specified time point, prior to dosing and prior to interaction with study personnel, to minimize missing data and subject bias.

[REDACTED]

[REDACTED]

## 7. DESCRIPTION OF STUDY TREATMENTS

### 7.1. Description of Investigational Product(s)

#### 7.1.1. AG-120

Celgene Corporation will supply AG-120, 250 mg strength tablets. Each tablet is formulated using excipients that are generally regarded as safe and are used in marketed drug products.

AG-120 tablets will be packaged in an appropriate container with child resistant closures and will be labeled appropriately as IP for this study.

Packaging and labeling will be prepared to meet all regulatory requirements.

Bottles of AG-120 tablets must be stored according to the package label. All investigational products must be stored in a secure, limited-access location and may be dispensed only by the investigator or by a member of the staff specifically authorized by the investigator.

#### 7.1.2. AG-221

Celgene Corporation will supply AG-221, 50-, 100-, and 200-mg free-base equivalent strength tablets for oral administration. Each tablet is formulated using excipients that are generally regarded as safe and are used in marketed drug products.

AG-221 tablets will be packaged in an appropriate container with child resistant closures and will be labeled appropriately as IP for this study.

Packaging and labeling will be prepared to meet all regulatory requirements.

Bottles of AG-221 tablets must be stored according to the package label. All investigational products must be stored in a secure, limited-access location and may be dispensed only by the investigator or by a member of the staff specifically authorized by the investigator.

#### 7.1.3. Azacitidine

Azacitidine will be supplied by Celgene Corporation as a sterile lyophilized powder containing 100 mg of azacitidine and 100 mg of mannitol per vial.

For subcutaneous administration, vials containing 100 mg of freeze-dried azacitidine will be reconstituted with 4 mL sterile water for injection. Azacitidine degrades rapidly at room temperature following reconstitution; therefore, the azacitidine suspension should be prepared immediately before use and the reconstituted suspension should be administered within 45 minutes. If elapsed time is greater than 45 minutes, the reconstituted suspension should be discarded appropriately and a new dose prepared. Alternatively, if the product needs to be reconstituted in advance of administration, it must be placed in a refrigerator (2°C to 8°C [36°F to 46°F]) immediately after reconstitution, and kept in the refrigerator for a maximum of 8 hours. If the elapsed time in the refrigerator is greater than 8 hours, the suspension should be discarded appropriately and a new dose prepared. The syringe filled with reconstituted suspension should be allowed up to 30 minutes prior to administration to reach a temperature of approximately 20°C to 25°C (70°F to 77°F). If the elapsed time is longer than 30 minutes, the suspension should be discarded appropriately and a new dose prepared.

Detailed instructions for preparation of SC azacitidine are provided in [Appendix H](#).

Azacitidine will be packaged and labeled appropriately as IP and will meet all regulatory requirements.

## 7.2. Treatment Administration and Schedule

The subject may not receive study treatment for each treatment cycle until all Day 1 procedures have been completed and all doses of study treatment from the prior treatment cycle have been accounted for (where applicable). For FCBP subjects, a serum or urine (investigator's discretion under local regulations)  $\beta$ -hCG pregnancy test (sensitivity of at least 25 mIU/mL) must be performed within 72 hours prior to study treatment administration on Day 1 of each treatment cycle and verified negative.

The first day of study treatment dosing is considered Day 1 of a cycle.

Subjects will be monitored for hematologic toxicity and non-hematologic toxicity with the Common Terminology Criteria for Adverse Events (CTCAE, Version 4.03) used as a guide for the grading of severity. Dosing interruptions or delays, or dose modifications may occur for managing toxicities and/or treatment response during study treatment.

**Overdose**, as defined for this protocol, refers to AG-120, AG-221, and azacitidine dosing.

On a per dose basis, an overdose is defined as the following amount over the protocol-specified dose of AG-120, AG-221, and azacitidine assigned to a given subject, regardless of any associated adverse events or sequelae.

PO any amount over the protocol-specified dose

SC 10% over the protocol-specified dose

On a schedule or frequency basis, an overdose is defined as anything more frequent than the protocol required schedule or frequency.

Complete data about drug administration, including any overdose, regardless of whether the overdose was accidental or intentional, should be reported in the case report form. See [Section 10](#) for the reporting of adverse events associated with overdose.

Subjects can continue to receive study treatment provided that they benefit from study treatment and have an acceptable toxicity profile. Study treatment can be discontinued if the investigator has alternative therapies (eg, HSCT) and/or considers study treatment to be no longer beneficial to the subject, or the rapidity of change of disease state renders it unacceptable for further study treatment in the judgment of the investigator.

Refer to [Section 11.1](#) for events that are considered sufficient reasons for discontinuing a subject from study treatment.

## **7.2.1. Treatment Administration**

### **7.2.1.1. Dispensation and Administration of AG-120 or AG-221**

#### Phase 1b Dose-finding and AG-120 Expansion Stage

AG-120 given at 500 mg in cohort 1 or 250 mg in cohort -1, orally QD on Days 1 – 28 of each 28-day cycle until treatment discontinuation (Section 11.1).

AG-221 is given at 100 mg in cohort 1, 200 mg in cohort 2, or 50 mg in cohort -1, orally QD on Days 1 – 28 of each 28-day cycle until treatment discontinuation (Section 11.1).

#### Phase 2 AG-221 Randomization Stage

AG-221 is given at the RCD orally QD on Days 1 – 28 of each 28-day cycle until treatment discontinuation (Section 11.1).

#### Phase 1b (Dose-finding and AG-120 Expansion) and Phase 2 AG-221 Radomomized Stage

AG-120 or AG-221 will be dispensed on Day 1 of each treatment cycle, with sufficient IP to complete a 28-day cycle. Subjects should be instructed to open AG-120 or AG-221 packaging as close as possible to when they are going to take AG-120 or AG-221, inspect each AG-120 or AG-221 tablet and only take tablets that are totally intact (subjects should be instructed to return any tablet not totally intact to the clinic).

Subjects should be instructed to take their daily dose at approximately the same time each day  $\pm$  6 hours. Each dose should be taken with a glass of water and consumed over as short a time as possible. Subjects should be instructed to swallow tablets whole and to not chew the tablets. Fasting is required for 2 hours prior to and 1 hour following AG-221 administration. Water is allowed during fasting. Fasting is not required for AG-120 administration.

All efforts should be made to administer AG-120 or AG-221 on all of the scheduled days of each 28-day treatment cycle. A dose missed earlier in a day can be made up later that day as long as it is taken within 6 hours after the missed dose. If more than 6 hours have elapsed, then that dose should be omitted, and the subject should resume treatment with the next scheduled dose. Any missed doses should be documented in the subject diary and not be taken beyond the last scheduled day of AG-120 or AG-221 administration, but should be returned by the subject for drug accountability.

If vomiting occurs shortly after a dose of AG-120 or AG-221 administrated, that dose should not be made up later that day. The subject should continue with the dosing schedule on the next day and inform the investigator about the vomiting event at the next visit and document this in the subject diary.

In order to optimally benefit from the treatment, investigators should aim to treat patients for at least 6 cycles, although patients can be discontinued from protocol earlier if they demonstrate unacceptable toxicity or relapse after CR or PR, transformation to AML, or disease progression.

### **7.2.1.2. Dispensation and Administration of Azacitidine**

SC azacitidine will be prepared as detailed in [Appendix H](#).

Subjects randomized to the azacitidine arm will receive azacitidine 75 mg/m^2/day SC for 7 days every 28 days until treatment discontinuation (Section 11.1). In addition, subjects may receive

BSC as needed (please refer to local prescribing information and local therapeutic guidelines for more details on available formulations, preparation, storage conditions [eg, refrigeration], the approved indications, known precautions, warnings, and adverse reactions of best supportive care; see current version of Prescribing Information), including antibiotics and transfusions, per investigator discretion. In the event 2 or fewer doses are missed during the 7-day dosing period, dosing should continue so the subject receives the full 7 days of therapy. If 3 or more days are missed during the 7-day dosing period, the investigator should contact the sponsor and a decision on dosing will be made on a case-by-case basis.

In order to optimally benefit from the treatment, investigators should aim to treat patients for at least 6 cycles, although patients can be discontinued from protocol earlier if they demonstrate unacceptable toxicity or relapse after CR or PR, transformation to AML, or disease progression.

### 7.2.2. Treatment Schedule

#### 7.2.2.1. Phase 1b Dose-finding Stage

The dose finding will use a “3 + 3” design. During the dose-finding phase, consented eligible subjects will be enrolled into one cohort of AG-120 or sequential cohorts of increasing doses of AG-221.

##### 7.2.2.1.1. AG-120 Cohorts

The dosing cohorts for subjects with an IDH1 gene mutation treated with AG-120 will be as follows:

**Table 9: AG-120 Cohorts**

Cohort	IDH1 mutant
	AG-120 dose
Cohort -1	250 mg QD
Cohort 1	500 mg QD

##### 7.2.2.1.2. AG-120 Expansion Stage

Phase 1b dosing of the AG-120 expansion cohort will be the RCD, as declared by the DRT, based on AG-120 + SC azacitidine data.

##### 7.2.2.1.3. AG-221 Cohorts

The dosing cohorts for subjects with IDH2 gene mutation treated with AG-221 will be as follows:

**Table 10: AG-221 Cohorts**

Cohort	IDH2 mutant
	AG-221dose
Cohort -1	50 mg QD
Cohort 1	100 mg QD

**Table 10: AG-221 Cohorts (Continued)**

Cohort	IDH2 mutant
	AG-221 dose
Cohort 2	200 mg QD

[figure not shown]
**7.2.2.1.4. Azacitidine**

The dosing for azacitidine will be 75 mg/m^2/day SC for 7 days of each 28-day cycle for all cohorts in both IDH1 and IDH2 gene mutation subjects.

**7.2.2.2. Phase 2 AG-221 Randomization Stage**

Randomization occurs via IWRS after confirming ongoing eligibility of the subject. All subjects randomized will be stratified by primary (ie, de novo) or secondary (progression of MDS or myeloproliferative neoplasms [MPN], or therapy-related) AML according to the WHO classification ([Appendix B](#)).

Oral AG-221 + SC azacitidine treatment arm will be initiated at the RCD of AG-221 on Days 1 - 28 of each 28-day treatment cycle. Both combination and single agent azacitidine will be administered at 75 mg/m^2/day SC for 7 days of each 28-day cycle. Pending the outcome of the Phase 1b dose-finding, a dose escalation of AG-221 to 200 mg daily may be initiated to augment treatment response as stated in Section [7.2.2.3.1](#) below.

**7.2.2.3.1. Dose Modifications for AG-120 or AG-221**

**Dose modification due to toxicities**

If a certain level of toxicity (eg, Section [7.2.2.3.2](#)) is observed after initiation of AG-120 or AG-221 treatment and is considered as possibly or probably related to treatment, dosing could be interrupted or delayed. Upon resolution of the toxicity, dosing may be resumed with a one-level dose reduction at the discretion of the investigator. Any subject who is unable to tolerate 250 mg QD of AG-120 or 50 mg QD of AG-221 should be discontinued from study treatment.

Refer to [Table 11](#) for sequential dose levels.

If treatment is modified during the course of the study and benefit is demonstrated after a reduced dose level, that dose level should be maintained during subsequent treatment cycles unless toxicity develops.

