#### **3.1.1.6. Phase 1b Treatment Period**

Eligible subjects will report to the study site to receive study treatment and protocol-specified procedures according to the [Table 4: Table of Events](#). The treatment period will consist of continuous 28-day cycles.

Subjects with newly diagnosed AML who are deemed by the investigator not candidates to receive intensive IC will be assigned to oral AG-120 + SC azacitidine or oral AG-221 + SC azacitidine depending on the IDH mutations (IDH1 or IDH2, respectively).

The discontinuation of AG-120, AG-221, or azacitidine for subjects in the combination arms of the study is allowed. Subjects may continue treatment with single agent AG-120, AG-221, or azacitidine if in the investigator's assessment the subject continues to show clinical benefit and all protocol-specified criteria for continuing study treatment are met.

All subjects may continue to receive study treatment until disease progression or unacceptable toxicity, withdrawal of consent, or end of the study. Subjects assigned to a lower dose cohort will

continue at their assigned dose throughout their participation in the study; dose escalation up to the RCD dose is not permitted.

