#### IDH2 Subjects

Arm 1: Oral AG-221 + SC azacitidine (66 Subjects)

Arm 2: SC azacitidine (33 Subjects)

Dose modifications and interruptions are permitted as detailed in Sections 7.2.2.3.1 and 7.2.2.3.4.

The discontinuation of AG-221 or azacitidine for subjects in the combination arms of the study is allowed. Subjects may continue treatment with single agent AG-221 or azacitidine if in the investigator's assessment the subject continues to show clinical benefit and all protocol-specified criteria for continuing study treatment are met.

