- If no other cause is identified and the investigator believes it is appropriate, particularly if QTc remains elevated (after above measures have been implemented, or as determined by the investigator), investigational product may be interrupted, and an ECG should be rechecked in approximately 1 week after the QTc prolongation was first observed, or more frequently as clinically indicated.
  - If QTc has recovered or improved and the investigator believes it is safe to do so, re-challenge with AG-120 or AG-221 should be considered if held. ECGs should be conducted at least weekly (eg, at every scheduled visit) for 2 weeks following QTc reduction  $\leq$  480 msec.
  - If Grade 2 (QTcF > 480 and  $\leq$  500 msec), the dose of AG-120 or AG-221 may be reduced to a dose approved by the medical monitor without interruption of dosing. The AG-120 or AG-221 dose may be re-escalated to the prior dose in  $\geq$  14 days after QT prolongation has decreased to  $\leq$  Grade 1.
  - If Grade 3 (QTcF > 500 msec), when QTc prolongation is first observed, hospitalization for continuous cardiac monitoring and evaluation by a cardiologist should both be considered. Dosing with AG-120 or AG-221 will be interrupted. If QTc returns to within 30 ms of baseline or < 450 msec within 14 days, treatment may be resumed at a reduced dose. The AG-120 or AG-221 dose cannot be re-escalated following dose reduction for Grade 3 QTcF prolongation

unless the prolongation was associated with an electrolyte abnormality or concomitant medication.

- If Grade 4 (QTcF > 500 msec or > 60 msec change from baseline with torsade de pointes or polymorphic ventricular tachycardia or signs/symptoms of serious arrhythmia), subjects should be admitted to hospital when QTc prolongation is first observed for continuous cardiac monitoring and be discharged only after review by a cardiologist. Dosing with AG-120 or AG-221 should be permanently discontinued.

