**Azacitidine Dose Modifications due to Nonhematological Toxicity**

Following receipt of any dose of azacitidine, subsequent treatment cycles may be delayed if a certain level of toxicity occurs after the previous dose. Any subject who experiences a non-hematological AE of Grade 3 or 4 that is an escalation from his or her status at baseline (Section 6.2.1) should have azacitidine temporarily discontinued until the toxicity Grade returns to less than Grade 3. Azacitidine should be permanently discontinued if the non-hematological toxicity persists as Grade 3 or 4 for more than 21 days, despite the temporary interruption of azacitidine.

Necrotising fasciitis, including fatal cases, have been reported in patients treated with azacitidine. Azacitidine therapy should be discontinued in patients who develop necrotising fasciitis, and appropriate treatment should be promptly initiated.

If azacitidine is permanently discontinued in the combination arms, AG-120 or AG-221 may continue at the discretion of the investigator.

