## 11. DISCONTINUATIONS

### 11.1. Treatment Discontinuation

The following events are considered sufficient reasons for discontinuing a subject from study treatment:

- Adverse event
- Progressive disease ([Appendix F](#))
- Withdrawal by subject from study treatment
- Discontinuation of all study drugs
- Death
- Lost to follow-up
- Allogeneic HSCT
- Pregnancy
- Other (to be specified on the eCRF)

The discontinuation of AG-120, AG-221, or azacitidine for subjects treated with the combination is allowed. Subjects may continue treatment with single agent AG-120, AG-221, or azacitidine if in the investigator's assessment the subject continues to show clinical benefit and all protocol-specified criteria for continuing study treatment are met.

Although progressive disease is considered a sufficient reason for discontinuing a subject from study treatment, the investigator may consider continuing study treatment until the investigator has alternative therapies (eg, allogeneic HSCT) and/or considers study treatment to be no longer beneficial to the subject, or the rapidity of change of disease state renders it unacceptable for further study treatment in the judgment of the investigator.

The decision to discontinue a subject from treatment remains the responsibility of the treating physician, which will not be delayed or refused by the Sponsor. However, prior to discontinuing a subject for progressive disease, or any other reason if not listed above, the investigator may contact the medical monitor and forward appropriate supporting documents for review and discussion. The reason for discontinuation of study treatment should be recorded in the eCRF and in the source documents.

[figure not shown]

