9.6. Dose Modification

The number of subjects who have at least one dose modification (interruption/reduction), number of dose modifications per subject, and reasons for dose modifications will be summarized by dose cohort (Phase 1b) or treatment arm (Phase 2). Details of dose adjustments will be provided in a by subject listing.

The discontinuation of AG-120, AG-221, or AZA for subjects in the combination arms of the study is allowed. Subjects may continue treatment with single agent AG-120, AG-221, or AZA if in the investigator's assessment the subject continues to show clinical benefit and all protocol-specified criteria for continuing study treatment are met. Number of subjects who discontinue one drug (AG-120, AG-221 or AZA) in combined treatment arms of AG-120 + AZA or AG-221 + AZA will be summarized.

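### Protocol 7.2.2.3.1, read literally, takes a subject who cannot tolerate the lowest AG-120 or AG-221 dose off azacitidine as well, although the rest of the protocol lets azacitidine continue alone

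*Protocol*

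**What the plan says.** Protocol Section 7.2.2.3.1 sets out interruption and one-level reduction of AG-120 or AG-221 for toxicity, and then gives the rule for a subject who has run out of dose levels: "Any subject who is unable to tolerate 250 mg QD of AG-120 or 50 mg QD of AG-221 should be discontinued from study treatment". It has no exception and no cross-reference.

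Other sections deal with stopping one component of the combination:

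- Section 3.1.1.6 (Phase 1b): "The discontinuation of AG-120, AG-221, or azacitidine for subjects in the combination arms of the study is allowed".
- Section 3.1.2.2 (Phase 2): "Subjects may continue treatment with single agent AG-221 or azacitidine if in the" investigator's view there is still clinical benefit and the protocol's criteria for continuing are met.
- Section 11.1 (Treatment Discontinuation): "The discontinuation of AG-120, AG-221, or azacitidine for subjects treated with the combination is allowed". The single-agent permission follows, on the same conditions.
- The Protocol Summary (Study Design) gives the same permission.
- SAP Section 9.6 repeats it and plans a summary: "Number of subjects who discontinue one drug (AG-120, AG-221 or AZA) in combined treatment arms".

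Two neighbouring rules name the drug concerned. For Grade 4 QTcF prolongation, Section 7.2.2.3.2 says: "Dosing with AG-120 or AG-221 should be permanently discontinued". For azacitidine toxicity, Section 7.2.2.3.4 says: "If azacitidine is permanently discontinued in the combination arms, AG-120 or AG-221 may continue at the discretion of the investigator".

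**The concern.** The sentence in 7.2.2.3.1 concerns toxicity attributed to the IDH inhibitor, but the action it orders is withdrawal from study treatment, with no drug named. A site that follows the words stops azacitidine, the drug that Arm 2 keeps receiving, because of a toxicity attributed to something else. A site that follows 11.1 may keep the subject on azacitidine.

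These subjects have newly diagnosed AML and are not candidates for intensive induction, so losing the backbone drug is a real matter of care. The choice also affects records. The End of Treatment visit is timed from stopping all study treatment (Sections 3.1.1.7 and 3.1.2.3). The 28-day adverse-event window runs from the last study treatment (Protocol 10.1, SAP 11.1). The SAP 9.6 count of single-drug stops would include the subject at one site and not at the other.

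**Working it through.** The plan states no figure for this rule, so the check is mainly a comparison of texts.

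**What study treatment means in this protocol.** Section 10.1 refers to the several drugs that make up study treatment. Section 11.1 lists stopping all study drugs among the reasons for ending it. The End of Treatment visit follows the end of all study treatment. In each place the term covers the regimen and not one component.

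**The rules side by side.**

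| Situation | Section | What stops | What may continue |
|---|---|---|---|
| Lowest inhibitor dose not tolerated | 7.2.2.3.1 | Study treatment | Nothing stated |
| Grade 4 QTcF prolongation | 7.2.2.3.2 | AG-120 or AG-221, by name | Azacitidine not mentioned as stopped |
| Azacitidine permanently stopped for non-hematologic toxicity | 7.2.2.3.4 | Azacitidine, by name | AG-120 or AG-221 |
| Any single-drug stop in the combination | Summary, 3.1.1.6, 3.1.2.2, 11.1; SAP 9.6 | One drug | The other, azacitidine included, on conditions |

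The first row is the odd one out. Taken literally, failing 50 mg of AG-221 ends both drugs, whereas a QT event with signs of serious arrhythmia ends only the inhibitor. Nothing in the documents supports that ordering.

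**Size for one subject.** Inputs:

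- Section 7.2.1.2: "investigators should aim to treat patients for at least 6 cycles".
- Azacitidine is given on 7 days of each cycle.
- The stop falls after Cycle 2 to Cycle 4. This is an assumption; the documents give no timing.

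Doses in the six-cycle aim: 6 × 7 = 42.

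- Stop after Cycle 2: 2 × 7 = 14 given, 42 − 14 = 28 forgone, 28/42 = 67%.
- Stop after Cycle 4: 4 × 7 = 28 given, 42 − 28 = 14 forgone, 14/42 = 33%.

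This supposes that the subject would otherwise qualify for single-agent azacitidine and take every dose on schedule.

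**Effect on the analysis.** The number of subjects affected cannot be computed without a rate of intolerance at the lowest dose, so no change in ORR is calculated. Three features suggest that it is small. A response before the stop still counts in the ITT analysis. Response assessment continues off treatment until progression, relapse or second-line therapy (Protocol 3.1.2.4, 6.3). For EFS, SAP 10.2.1 includes a sensitivity analysis, EFS2, that counts events after subsequent AML therapy.

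**The case against.** The best answer is that context settles the meaning. The section is headed for AG-120 and AG-221 only, the table it points to lists inhibitor doses only, and azacitidine has its own section. Section 7.2 sends the reader to 11.1 for reasons to discontinue, and 11.1 permits azacitidine alone. Section 7.2.2.3.2 also uses a broad term loosely: it speaks of interrupting investigational product and then of re-challenge with the inhibitor, although azacitidine is investigational product too. One loose sentence stands against five explicit statements, and the documents show no site that misread it.

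This is good evidence of intent, and stopping only the inhibitor is the likelier intent. It does not change the operative words, and it is a reason to correct them.

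A second argument is that there is no strict contradiction. Single-agent continuation depends on meeting the protocol's criteria for continuing, and the 7.2.2.3.1 sentence could be one of those criteria. No section says so. If it were, azacitidine would be withdrawn for inhibitor toxicity, which is the outcome complained of.

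The remarks on size are fair. Six cycles is a minimum aim, the stopping time is assumed, and a Phase 2 subject starting at 100 mg must first be reduced to 50 mg and then fail that dose. The latest amendment's justification also reports that the primary-analysis report was final and that 15 subjects (4 on AG-120, 11 on AG-221) remained on treatment at 15 March 2021. Prospective reach is therefore limited, though all 15 were on a combination. It is also right that this is a fault of wording more than a choice of design.

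**Conclusion.** The concern holds on the literal reading. Section 7.2.2.3.1 orders withdrawal from the whole regimen, while the Protocol Summary, three other protocol sections and the SAP let azacitidine continue. The sentence is wrong as written and should be corrected.

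The number of subjects affected is unknown. For one subject the literal rule costs 14 to 28 of 42 azacitidine doses, under the assumed stop between the end of Cycle 2 and the end of Cycle 4. No material effect on the ITT response rate is claimed, and the analysis set, sample size, power and alpha are untouched. What is at stake is the subject's care and uniform handling across sites.

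**What to change.** In Section 7.2.2.3.1, replace the end of the sentence so that such a subject *should permanently discontinue AG-120 or AG-221; azacitidine may continue as a single agent under Sections 3.1.1.6, 3.1.2.2 and 11.1.* If the sponsor does intend full withdrawal, the sentence should say that azacitidine also stops, and 11.1 should carry the exception.

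The recommended change costs one phrase in the protocol. No new eCRF field or SAP change is needed: dosing is already recorded (Protocol 7.6), exposure is summarised by compound (SAP 9.1, 9.3), and single-drug stops are already counted (SAP 9.6).
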